7. DISCONTINUATION OF STUDY INTERVENTION AND PARTICIPANT DISCONTINUATION/WITHDRAWAL

Discontinuation of specific sites or of the study as a whole are detailed in Section 10.1.10.

7.1. Discontinuation of Study Intervention

In rare instances, it may be necessary for a participant to permanently discontinue study intervention. If study intervention is permanently discontinued, the participant should, if at all possible, remain in the study for follow-up and for any further evaluations that need to be completed (see the SoA [Table 1]).

7.2. Participant Discontinuation/Withdrawal from the Study

- A participant may withdraw from the study at any time at the participant's own request for any reason (or without providing any reason).
- A participant may be withdrawn at any time at the discretion of the Investigator for safety, behavioral, or compliance reasons.
- At the time of discontinuing from the study, if possible, an end of study call should be conducted, as shown in the SoA (Table 1). See the SoA for data to be collected at the time of study discontinuation and follow-up and for any further evaluations that need to be completed.
- The participant will be permanently discontinued from the study intervention and the study at that time.
- A participant who withdraws from the study will not be replaced.
- If the participant withdraws consent for disclosure of future information, the Sponsor may retain and continue to use any data collected before such a withdrawal of consent.
- If a participant withdraws from the study, the participant may request destruction of any samples taken and not tested, and the Investigator must document this in the site study records.
- The Sponsor will continue to retain and use all research results that have already been collected for the study evaluation. All biological samples that have already been collected may be retained and analyzed at a later date (or as permitted by local regulations).

From an analysis perspective, a "withdrawal" from the study refers to a situation wherein a participant does not return for the final visit foreseen in the protocol. All data collected until the date of withdrawal or last contact of the participant will be used for the analysis. A participant is considered a "withdrawal" from the study when no study procedure has occurred, no follow-up has been performed, and no further information has been collected for that participant from the date of withdrawal or last contact.

Information relative to the withdrawal will be documented in EDC. The Investigator will document whether the decision to withdraw a participant from the study was made by a

participant, or by the Investigator, as well as which of the following possible reasons was responsible for withdrawal:

- AE
- Death
- Lack of efficacy
- Lost to follow-up
- Noncompliance with study intervention
- Other
- Physician decision
- Protocol deviation
- Screen failure
- Study terminated by Sponsor
- Withdrawal by participant
- Withdrawal due to solicited ARs/reactogenicity

Participants who are withdrawn from the study because of SAEs/AEs must be clearly distinguished from participants who are withdrawn for other reasons. Investigators will follow-up with participants who are withdrawn from the study because of an SAE or AE until resolution of the event.

7.3. Lost to Follow-up

If a participant does not complete a visit within the time window specified in the SoA (Table 1), every effort should still be made to complete the assessments for that visit (even though outside of the defined visit window); the participant will continue with subsequent scheduled study visits per their original schedule (ie, relative to their Day 1 visit). If a participant still does not complete the visit after all these efforts, the visit will be classified as missed and all safety requirements of the missed visit will be captured and included in the subsequent visit.

A participant will be considered lost to follow-up if the participant repeatedly fails to return for scheduled visits and is unable to be contacted by the study site.

The following actions must be taken if a participant fails to return to the clinic for a required study visit:

- The site must attempt to contact the participant and reschedule the missed visit as soon as possible, counsel the participant on the importance of maintaining the assigned visit schedule and ascertain whether the participant wishes to and/or should continue in the study.
- Before a participant is deemed lost to follow-up, the Investigator or designee must make every effort to regain contact with the participant (where possible, 3 telephone calls, and if necessary, a certified letter to the participant's last known mailing

mRNA-1345

address or local equivalent methods). These contact attempts should be documented in the participant's medical record.

- Should the participant continue to be unreachable, the participant will be considered to have withdrawn from the study.
- A participant should not be considered lost to follow-up until due diligence has been completed.

7.4. Pause Rules

Not applicable.

8. STUDY ASSESSMENTS AND PROCEDURES

- Study procedures and their timing are summarized in the SoA (Table 1). Protocol waivers or exemptions are not allowed.
- Adherence to the study design requirements, including those specified in the SoA (Table 1), is essential and required for study conduct.
- All screening evaluations must be completed and reviewed to confirm that potential participants meet all eligibility criteria. The Investigator will maintain a screening log to record details of all participants screened and to confirm eligibility or record reasons for screening failure, as applicable.
- Procedures conducted as part of the participant's routine clinical management (eg, blood count) and obtained before signing of the ICF may be utilized for screening or baseline purposes provided the procedures met the protocol-specified criteria and were performed within the timeframe defined in the SoA (Table 1).
- In the event of a significant study-continuity issue (eg, caused by a pandemic), alternate strategies for participant visits, assessments, medication distribution, and monitoring may be implemented by the Sponsor or the Investigator, as per local health authority/ethics requirements.
- Study results that could unblind the study will not be reported to investigative sites or other blinded personnel until the study has been unblinded.
- If a visit cannot be scheduled within the indicated allowable window and/or the participant misses the visit, this is considered a protocol deviation. However, the visit should still be completed, if possible, to collect study data. Subsequent visits should be scheduled at the originally planned number of days after Day 1 defined in the SoA (Table 1).

The maximum amount of blood collected from each participant over the duration of the study, including any extra assessments that may be required, will not exceed blood limits specified by local regulations. Sample collection on Day 1 and Day 22 (ie, blood) must be performed prior to study intervention dosing.

Repeat or unscheduled samples may be taken for safety reasons or for technical issues with the samples. Further details are provided in both the ICF and Laboratory Reference Manual.

8.1. Demography

Demographic information relating to the participant's sex, age, and race will be recorded at Screening in EDC.

The medical history of each participant will be collected and recorded in EDC. Significant findings that were present prior to the signature of the informed consent will also be included in EDC.

8.2. Immunogenicity Assessments

Blood samples for immunogenicity assessments will be collected at the time points indicated in the SoA (Table 1). Immunogenicity assessments will be performed for all participants. The following analytes may be measured:

- RSV serum Abs, including nAbs and bAbs.
- Influenza virus serum Abs, measured by HAI assay.

Sample aliquots will be designed to ensure that backup samples are available and vial volumes are likely to be adequate for future testing needs. The actual date and time of each sample will be noted. Unique sample identification will be utilized to maintain the blind at the laboratory at all times and allow for automated sample tracking and housing. Handling and preparation of the samples for analysis, as well as shipping and storage requirements, will be provided in a separate study manual.

Measurement of Ab levels will be performed in a laboratory designated by the Sponsor.

According to the ICF (Section 10.1.3), excess serum from the blood samples collected for immunogenicity testing may be used for future research, which may be performed at the discretion of the Sponsor to further characterize the immune response to RSV and influenza virus and for additional assay development.

8.3. Safety Assessments

Safety assessments will include monitoring and recording of the following for each participant according to the SoA (Table 1):

- Solicited local and systemic ARs that occur during the 7 days following each vaccine administration (ie, the day of study intervention dosing and 6 subsequent days [Days 1-7 and Days 22-28]). Solicited ARs will be recorded daily using eDiaries. Local solicited ARs will be recorded separately for each injection site. eDiary review by the site should occur daily on Day 1-Day 7 and Day 22-28. Additional review of the eDiary will occur at Day 8 and Day 29 between the site and the participant during the safety telephone calls.
- Unsolicited AEs observed or reported from the day of each injection and 20 subsequent days. Unsolicited AEs are AEs that are not included in the protocoldefined solicited ARs.
- SAEs from the time of signing ICF through Month 6 (EoS) after the last study intervention dosing.
- AESIs, MAAEs, and AEs leading to discontinuation from study participation from vaccination on Day 1 through Month 6 after the last study intervention dosing (EoS) or withdrawal from the study.
- Vital sign measurements
- Physical examination findings
- Concomitant medications and nonstudy vaccinations

• Concomitant procedures

8.3.1. Physical Examinations

A complete physical examination, including height and weight, will be performed at the Screening Visit. A complete physical examination is not needed on Day 1 if Screening occurs within 7 days of Day 1.

- A complete physical examination will include, at a minimum, assessments of the cardiovascular, respiratory, gastrointestinal, and neurological systems. Height and weight will also be measured and recorded.
- Investigators should pay special attention to clinical signs related to previous serious illnesses.
- On the day of study intervention administration, before administration, the arms receiving the injection(s) should be examined and the associated lymph nodes should be evaluated.

Any clinically significant finding identified during the Screening Visit should be reported as medical history, and during study visits should be reported as a MAAE.

Symptom-directed physical examinations will be performed at other in-person visits, if clinically indicated (Table 1). Any clinically significant finding identified during a symptom-directed physical examination should be reported as an AE.

Investigators should pay special attention to clinical signs related to previous serious illnesses.

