3. OBJECTIVES AND ENDPOINTS

Table 2: Objectives and Endpoints

Objectives	Endpoints		
Primary	-		
To evaluate the safety and reactogenicity of mRNA-1345 RSV vaccine coadministered with a HD quadrivalent seasonal influenza vaccine (Fluzone HD).	 Solicited local and systemic ARs through 7 days after each injection. Unsolicited AEs through 21 days after each study injection. MAAEs from Day 1 to Month 6 after last study injection/EoS. AESI from Day 1 to Month 6 after last study injection/EoS. SAEs from Day 1 to Month 6 after last study injection/EoS. AEs leading to discontinuation from Day 1 to Month 6 after last study injection/EoS. 		
To evaluate the impact of coadministered HD quadrivalent seasonal influenza vaccine on the immune response to mRNA-1345 RSV vaccine against RSV-A and RSV-B.	GMT of serum RSV-A and RSV-B nAbs at Day 22 (Arm 1 a) or Day 43 (Arm 2 b).		
To evaluate the impact of coadministered mRNA-1345 RSV vaccine on the immune response to HD quadrivalent seasonal influenza vaccine against 4 vaccine-matched influenza A and B strains.	GMT of serum anti-HA Ab level as measured by HAI assay at Day 22.		
Secondary			
To further evaluate the effect of mRNA-1345 RSV vaccine coadministered with a HD quadrivalent seasonal influenza vaccine on the immune response to RSV-A and RSV-B.	 SRR c in RSV-A and RSV-B nAbs at Day 22 (Arm 1) or Day 43 (Arm 2). GMFR of postinjection RSV-A and RSV-B nAbs (Day 22 for Arm 1 and Day 43 for Arm 2) compared to baseline (Day 1 for Arm 1 and Day 22 for Arm 2). Proportion of participants with ≥2-fold increase in RSV-A and RSV-B nAbs at Day 22 (Arm 1) or Day 43 (Arm 2). 		

Objectives	Endpoints
To further evaluate the effect of mRNA-1345 RSV vaccine coadministered with a HD quadrivalent seasonal influenza vaccine on the immune response against 4 vaccine- matched influenza A and B strains.	 SCR ^d at Day 22 as measured by HAI assay. GMFR comparing Day 1 (baseline) and Day 22 measured by HAI assay.
Exploratory (may be performed)	
To further evaluate the immune response across study vaccines.	GMC and GMFR of postinjection/baseline titers of RSV bAbs.
	• Proportion of participants with ≥2-fold and ≥4-fold increases in RSV bAb concentration postinjection.
	Frequency, specificities, or other endpoints to be determined, for the further characterization of immune responses.

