8.4.1. Time Period and Frequency for Collecting AE and SAE Information

All SAEs will be collected from the time of signing ICF through Month 6 after last study injection/EoS. AESI, MAAEs, and AEs leading to discontinuation from study participation will be collected from the start of study intervention dosing until Month 6 after each study injection (EoS) or withdrawal from the study, at the timepoints specified in the SoA (Table 1).

All solicited local and systemic ARs will be collected 7 days after study intervention dosing on Day 1 and Day 22 (ie, the day of study intervention dosing and 6 subsequent days).

All unsolicited AEs will be collected through the 21 days following each study intervention dosing (ie, the day of study intervention dosing and 20 subsequent days).

Medical occurrences that begin before the start of study intervention but after obtaining informed consent (and that are not SAEs) will be recorded as medical history/current medical conditions, not as AEs; however, if the condition worsens at any time after study intervention administration, it will be recorded and reported as an AE.

All SAEs will be recorded and reported to the Sponsor or designee immediately and under no circumstance should this exceed 24 hours. The Investigator will submit any updated SAE data to the Sponsor within 24 hours of it being available.

Investigators are not obligated to actively seek information on AEs or SAEs after conclusion of the study participation. However, if the Investigator learns of any SAE, including a death, at any time after a participant has been discharged from the study, and the Investigator considers the event to be reasonably related to the study intervention or study participation, the Investigator must promptly notify the Sponsor.

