8.4.6. Medically Attended Adverse Events

A MAAE is an AE that leads to an unscheduled visit to a healthcare practitioner. This would include visits to a study site for unscheduled assessments (eg, rash assessment, abnormal laboratory follow-up) and visits to healthcare practitioners external to the study site (eg, emergency room, urgent care, primary care physician). Investigators will review unsolicited AEs for the occurrence of any MAAEs. Unsolicited AEs will be captured in EDC.

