10.2.3. Definition of MAAE

A MAAE is an AE that leads to an USV to a healthcare practitioner. This would include visits to a study site for unscheduled assessments not required per protocol (e.g., rash assessment, abnormal laboratory follow-up) and visits to healthcare practitioners external to the study site (e.g., emergency room, urgent care, primary care physician).

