6.3.2. Adverse Events

An AE is any untoward medical occurrence in a clinical study participant, temporally associated with the use of study intervention, whether or not considered related to the study intervention. An AE can therefore be any unfavorable and unintended sign (including an abnormal laboratory finding), symptom, or disease (new or exacerbated) temporally associated with the use of study intervention. AEs will also be evaluated by the investigator for the coexistence of MAAE which is defined as an AE that leads to an unscheduled visit to a healthcare practitioner (HCP).

For analysis purpose, an AE is defined as any event occurring during the study but not present before exposure to study vaccine. Worsening of a pre-existing condition after vaccination will be reported as a new AE.

An unsolicited AE is any AE reported by the participant that is not specified as a solicited AR in the protocol or is specified as a solicited AR but starts outside the protocol-defined period for

reporting solicited ARs (i.e., 7 days after each study injection). For analysis and reporting purpose, unsolicited AEs will include the following:

- AEs that are reported by participants and recorded on the AE eCRF
- Solicited ARs that meet SAE criteria or last beyond 7 days after each injection and are recorded on the Reactogenicity eCRF

Unsolicited AEs will be collected for up to 21 days after each injection; SAEs, MAAEs, AESIs, and AEs leading to study discontinuation will be collected throughout the study. Unsolicited AEs will be summarized up to 21 days separately after Day 1 injection and Day 22 injection unless otherwise specified. Additionally, SAEs, MAAEs, AESIs and AEs leading to study discontinuation will be summarized throughout the study (up to Day 202/EoS). Refer to Safety Estimand 3b in Appendix G, Table 6.

All summary tables (except for the overall summary of AEs) for unsolicited AEs will be presented by SOC and PT (or by PT). SOC will be displayed in internationally agreed order. PTs will be displayed in descending order of frequency in the "D1: Fluzone HD+mRNA-1345 (pug) and D22: placebo" group and then alphabetically within SOC. When summarizing the number and percentage of participants with an event, participants with multiple occurrences of the same AE or a continuing AE will be counted once.

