Rationale for Strategies	This estimand seeks to understand immune response impact during the coadministered HD quadrivalent seasonal influenza vaccine in adults aged 65 or older who receive the assigned intervention dose at both Day 1 and Day 22 and comply with key protocol criteria. A principal stratum is used to exclude participants with prohibited medications affecting immune responses or important protocol deviations impacting key study data so that analysis is a sub-population composed of participants free from such intercurrent events. For early discontinuation, all collected data are included. Immunogenicity assessments falling out of visit window are excluded.	A treatment policy strategy is used for following up immune response including all participants who receive any study intervention dose irrespective of whether they subsequently were found not to strictly meet the key protocol criteria. There is interest in understanding immune response in the light of poor compliance which may happen in clinical practice.
--------------------------	---	--

Table 6: Summary of Primary Safety Estimands with Rationale for Strategies to Address Intercurrent Events

Objective: To evalua vaccine (Fluzone® H	te the safety and tolerability of mRNA-1345 RSV vaccine cosID)	administered with a HD quadrivalent seasonal influenza
Estimand Label	Safety Estimand 3a	Safety Estimand 3b
Estimand Description	Proportion of participants reporting any solicited local ARs up to 7 days after each study injection (Day 1 or Day 22).	Proportion of participants reporting any unsolicited AEs up to 21 days after each study injection (Day 1 or Day 22).
	• Proportion of participants reporting any solicited systemic ARs up to 7 days after each study injection	 Proportion of participants reporting any MAAEs up to Day 202/EOS.
	(Day 1 or Day 22).	 Proportion of participants reporting any AESI up to Day 202/EOS.
		 Proportion of participants reporting any SAEs up to Day 202/EOS.
		 Proportion of participants reporting any AEs leading to discontinuation from the study up to Day 202/EOS.
Target Population	Adults ≥65 years old who receive any study intervention and contribute any solicited AR data.	Adults ≥65 years old who receive any study intervention.
Endpoint	• Incidence of solicited local ARs up to 7 days after each study injection.	Incidence of unsolicited AEs up to 21 days after each study injection.

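### Protocol 8.3.1 tells sites to report examination findings at study visits as MAAEs, which conflicts with the MAAE definition used everywhere else and could over-label events in a primary safety endpoint

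*Protocol*

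**What the plan says.** Protocol 8.3.1 (Physical Examinations) gives two reporting rules. The first sends Screening findings to medical history and says that a clinically significant finding "during study visits should be reported as a MAAE". The second, in the next paragraph, reads: "Any clinically significant finding identified during a symptom-directed physical examination should be reported as an AE".

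Protocol 8.4.6 gives the definition: "A MAAE is an AE that leads to an unscheduled visit to a healthcare practitioner". Protocol 10.2.3 repeats it and, for contacts at the study site, counts only "visits to a study site for unscheduled assessments not required per protocol". SAP 6.3.2 uses the same definition.

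Protocol 8.4.1 says that non-serious events starting after consent but before study intervention "will be recorded as medical history/current medical conditions, not as AEs". It starts MAAE collection at dosing.

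The endpoint is primary. Protocol Section 3 lists "MAAEs from Day 1 to Month 6 after last study injection/EoS" under the primary safety objective. SAP Appendix G, Safety Estimand 3b, summarises it by treatment group as "Proportion of participants reporting any MAAEs up to Day 202/EOS".

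**The concern.** The first rule in 8.3.1 makes a finding a MAAE because of where it was seen. The definition makes an event a MAAE because of what it led to. A finding noted at a planned visit, with no further contact sought, is a MAAE under the first and not under the second.

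A site has grounds in the protocol for either reading. If sites choose differently, the MAAE proportion partly measures which section a site followed. If many follow 8.3.1, the category takes in events that needed no medical attention, and the events that did are harder to see. Reviewers will judge safety from these descriptive proportions and from the MAAE tables by system organ class and preferred term (SAP 6.3.2.2).

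**Working it through.** There is no stated figure to reproduce, because the documents give no rate of examination findings. The check is to see which rule governs each examination after Screening.

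| Examination | Depends on symptoms? | First rule of 8.3.1 | Other text |
|---|---|---|---|
| Day 1, before injection: arms and nodes; also a complete examination unless Screening was within 7 days | No | MAAE | 8.4.1: medical history if non-serious |
| Day 22, before injection: arms and nodes | No | MAAE | 10.2.3: not a MAAE without an unscheduled contact |
| Symptom-directed examination at a scheduled in-person visit | Yes | MAAE | Next paragraph of 8.3.1: AE |

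**Symptom-directed examinations.** The schedule's footnote makes examinations after Screening symptom-directed, if clinically indicated. The second rule is the more specific one, and a careful site would report an AE. The two sentences still need reconciling, but the likely harm here is small.

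**Day 1 before dosing.** 8.3.1 conflicts with 8.4.1. For analysis, SAP 6.3.2 counts only events not present before exposure to study vaccine. A finding recorded as preceding the injection should therefore drop out, whatever label the site gave it.

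**Day 22 before injection.** 8.3.1 calls for the arm and node check on each dosing day, with or without symptoms. The second rule does not reach it, and the SAP's pre-exposure exclusion does not remove a finding that arose after Day 1. Only the MAAE sentence speaks directly to it, and that sentence contradicts 8.4.6 and 10.2.3. This is the main place where the conflict has effect.

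**Correction downstream.** The SAP describes no step that re-derives MAAE status from a recorded unscheduled visit. Its statement in Section 1 that the SAP prevails concerns analysis methods, not what sites report.

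**Scale, by assumption only.** Let f be the share of participants with such a finding and no true MAAE, and s the share of them at sites that follow 8.3.1 literally. Extra participants labelled per arm = 950 × f × s. With s = 1:

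- f = 0.5%: 950 × 0.005 = 4.75
- f = 2%: 950 × 0.02 = 19
- f = 5%: 950 × 0.05 = 47.5

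With s = 0 the number is zero. Neither f nor s has a source in the documents, so these figures only convert an assumption into a count.

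**The case against.** The strongest reply is that one loose sentence stands against three consistent definitions. Protocol 8.4.6 has investigators review unsolicited AEs for MAAEs, and SAP 6.3.2 has them evaluate AEs for MAAE status with the definition alongside. Most post-Screening examinations are symptom-directed and fall under the AE rule. Pre-dose Day 1 findings are outside the collection period and the SAP's AE definition. The eCRF completion guidelines, which are not among the documents, may already settle the matter. The error adds a label rather than hiding an event, since unsolicited AEs are recorded at Day 1, Day 22 and Day 43.

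Most of this stands, and it narrows the point. It does not remove it. The investigator who applies the definition is the same person whom 8.3.1 instructs otherwise, and nothing in the documents says which text governs the Day 22 check. One might add that a MAAE is also an AE, so the two rules in 8.3.1 are compatible. But neighbouring sentences that name different categories will be read as different instructions.

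A reader might infer that the error favours one arm. The Day 22 check follows mRNA-1345 in Arm 1 but only Fluzone HD plus placebo in Arm 2, and the schedule lists no physical examination at Day 43, after Arm 2's mRNA-1345 dose. Blinding does not remove that asymmetry. However, the documents give no rate of arm or node findings three weeks after injection, so a difference between arms is a possibility and not a finding.

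**Conclusion.** The conflict is in the current text and should be corrected. Sites that follow 8.3.1 literally could over-label AEs as MAAEs in a primary safety endpoint, and practice could differ between sites. The exposure is mainly the Day 22 pre-injection check. This assumes that at least some sites act on the sentence as written and that no guidance outside these documents overrides it.

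The size cannot be estimated. Two stronger readings are tempting and go too far. One is that the MAAE rate will be inflated by a stated number of points: no document supplies the rate, and the effect depends on site practice. The other is that pre-dose events will be counted in the endpoint: SAP 6.3.2 should exclude them. MAAEs carry no hypothesis test, so the coprimary immunogenicity tests, power and alpha are untouched.

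**What to change.** In Protocol 8.3.1, replace the MAAE instruction for study-visit findings with wording such as: *should be reported as an AE if onset or worsening is after the first injection (as medical history if before it and not serious), and as a MAAE only if the definition in Section 10.2.3 is met.* Align the eCRF completion guidelines with it.

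The cost is a one-sentence protocol clarification and a note to sites. The SAP's analyses need no change. If sites have already worked under the present sentence, MAAE entries from scheduled visits with no recorded unscheduled contact could be queried before the data are locked for the primary analysis.
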